Participants will be hospitalized for at least 3 days or up to 7 days, depending on the participant convenience. After discharge, subjects will return daily to the Clinical Center for further assessments until Day 7. The duration of involvement in the study from day 0 (day of administration of first PZQ dose) will be 7 days. The start of the trial is defined as the date of the first visit (i.e. screening visit) of the first participant. The end of the trial is the date of the last visit of the last participant.

Potential risks for participants

Phlebotomy

The maximum volume of blood drawn over the study period is approximately 61 ml over 7 days. Additional blood samples could be required for safety reasons. However, this volume should not compromise these otherwise healthy participants. There may be minor bruising, local tenderness or presyncopal symptoms associated with venepuncture, which will not be documented as AEs if they occur. Rare side effects are infections, thrombophlebitis and neural lesions. In the case a participant develops severe discomfort from repeated venepunctures, and only with the recommendation/concurrence of the clinical team, an intravenous catheter could be inserted in one of the upper limbs of the participant to take the remaining blood samples as per protocol. An additional 2 mL of blood will be taken with each blood drawn when using the intravenous catheter. The participant will be informed about this extra volume of blood to be drawn before the catheter insertion.

Praziquantel

Side effects of praziquantel include nausea ($\geq 10\%$), vomiting ($\geq 10\%$), gastrointestinal and abdominal pain ($\geq 10\%$), headache ($\geq 10\%$), drowsiness ($\geq 10\%$), urticaria ($\geq 10\%$), diarrhoea

(<10%), anorexia (<10%), dizziness (<10%), somnolence (<10%), fever (<10%), rash (<10%), myalgia (<10%), unspecific arrhythmia (<0.0001%), pruritus (<0.0001%), seizure (<0.0001%), allergic reaction (<0.0001%), eosinophilia (<0.0001%) (41).

Potential benefits for participants

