The procedures to be included in each visit are documented in Table 2. In General, during the treatment period (D0-D2) each visit is assigned a time point and a window period of ± 2 hours within which the visit will be conducted. Only the visits with study drug dosing time points (i.e. H0, H24, H48) are exempted from this and have a stricter window period of ± 1 hour. Between D3 and D7 the visit can be performed at any given timepoint on the respective day considering participant and study team convenience. Patients must be seen for all visits on the designated day within the given window period, or as close to it as possible. Missed or rescheduled visits should not lead to automatic discontinuation.

Screening visit

All potential participants will have a screening visit, which shall take place on the same day (i.e. within 24 hours) as the administration of study drugs. Informed consent will be obtained from those eligible as described above. Once the informed consent is signed, the following screening procedures indicated in Table 2 will be undertaken:

- Full medical history, clinical examination (including measurement of height and weight) and ascertainment of demographic details
- Vital signs (pulse, blood pressure and temperature);
- urine β -HCG test in female participants;
- Blood samples will be taken for full blood count, biochemistry, thick and thin blood smears, blood for RNA later.
- The inclusion and exclusion criteria for the study will be assessed

AEs will be recorded from the signature of the informed consent onwards. Abnormal clinical findings from the medical history, vital signs assessment or blood tests at any point in the study will be assessed using established reference intervals of CERMEL laboratory. If a laboratory test is out of range it may be repeated to ensure it is not a single occurrence. If an abnormal finding is deemed to be clinically significant, the participant will be informed and appropriate medical care arranged with the permission of the participant.

Study drug administration (D0-D2; H0, H24 and H48)

Medication will take place at CERMEL and participants will be hospitalized for 3 days. Before the medication is administered the following measures will be performed on all participant:

- Vital signs
- Thick and thin blood smears
- Blood in RNA later
- Potential adverse events (AEs)
- Potential concomitant medication is ascertained

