- Clinical examination (Note that it does not need to be performed at H0, since it was performed just hours earlier during the screening visit)

Afterwards study medication is administered.

Time of hospitalization (D0-D2)

From the administration of the first dose of study medication (D0; H0) participants will be seen in 6-hourly intervals. These intervals continue until D2 (H66) when the patient can be discharged. The following assessments will be performed:

- Vital signs
- Thick and thin blood smears
- Blood in RNA later
- Potential adverse events (AEs)
- Potential concomitant medication is ascertained

Days 3-7

During D3-D7 participants are seen once daily. The following assessments will be performed per visit:

- Vital signs
- Thick and thin blood smears

- Blood in RNA later
- Potential adverse events (AEs)
- Potential concomitant medication is ascertained
- Clinical examination

Blood samples will be taken for full blood count and biochemistry on D3 and D7

Days 7 – end of study

After the performance of all assessments on D7 (i.e. at the end of the study), the rescue treatment (artemether/lumefantrine) will be given to all study participants irrespective of results in parasitaemia. This ensures that all study participants will reach complete parasite clearance. In accordance with national guidelines, six weight-adjusted doses of the rescue treatment will be given to study participants including an explanation on how to self-administer the medication at home.

Treatment of *Plasmodium falciparum* Infection:

The following circumstances warrant discontinuation of study treatment and the implementation of rescue medication:

- Any parasitaemia based on microscopy with fever post-dose
- Development of complicated signs or severe malaria on any day between Study Day 0 and Day 7 in the presence of parasitaemia.
- Investigator judgment

If applicable: Rescue medication according to local guidance will be used for severe malaria.

Table 2: Study procedures. Safety related procedures may be added if clinical investigator or the local safety monitor consider it necessary.

Visit (days)	Screening	D0				D1				D2				D3	D4	D5	D6	D7	UNS
Visit (hours)		H0 ± 1h	H6 ± 2h	H12 ± 2h	H18 ± 2h	H24 ± 1h	H30 ± 2h	H36 ± 2h	H42 ± 2h	H48 ± 1h	H54 ± 2h	H60 ± 2h	H66 ± 2h						
Demographics, medical history	x																		
Clinical examination	x					x				x				x	x	x	x	x	x
Vital signs*	x	x	x	x	x	x	x	x	x	x	x	x	x	x	x	x	x	x	(x)
Incl./Excl. criteria	x																		

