Urine β-HCG	x									x									(x)
'Adverse events' and 'concomitant medication'		x	x	x	x	x	x	x	x	x	x	x	x	x	x	x	x	x	x
Study drug administration		x				x				x									
Malaria rescue treatment																			(x)
Full blood count (1.2ml)	x													x				x	(x)
Biochemistry** (2.7ml)	x													x				x	(x)
Thick and thin blood smears (0.2ml)	x	x	x	x	x	x	x	x	x	x	x	x	x	x	x	x	x	x	x
Blood in RNA later (0.5ml)	x	x	x	x	x	x	x	x	x	x	x	x	x	x	x	x	x	x	x
Blood volume (total = 24.3 ml)	4.6 ml	0.7 ml	0.7 ml	0.7 ml	0.7 ml	0.7 ml	0.7 ml	0.7 ml	0.7 ml	0.7 ml	0.7 ml	0.7 ml	0.7 ml	4.6 ml	0.7 ml	0.7 ml	0.7 ml	4.6 ml	

(x) = if judged necessary by clinical investigator; Note that additional assessments at other time points may be performed if judged medically necessary by the clinical investigator

* Including pulse, blood pressure, temperature;

** Biochemistry: Aspartate aminotransferase (AST), alanine aminotransferase (ALT), alkaline phosphatase, gamma-glutamyltransferase (GGT), total bilirubin, conjugate bilirubin, albumin, lactate dehydrogenase (LDH), creatinine, urea, glucose, sodium, potassium, calcium, and magnesium

Assessment of safety

Safety of PZQ treatment will be assessed by analysing the frequency, incidence and nature of adverse events and serious adverse events arising during the study.

Definitions

Adverse Event (AE)

An Adverse Event (AE) is any new unfavourable and unintended sign, symptom, or disease temporally associated with the use of a medical treatment or procedure that may or may not be considered related to the medical treatment or procedure. An AE is a term that is a unique representation of a specific event used for medical documentation and scientific analyses. Each AE has to be documented in order of appearance, given by a number. In addition, the start and end time of the AE has to be noted precisely. The investigator must enter the information within 24 hours in the paper-based source document and eCRF using the AE section.

The term 'new' unfavourable and unintended sign/symptom/disease implies that this 'new' sign/symptom/disease was not present at baseline or was not part of the past medical history of the participant.

Example: In case a patient reports sleeping problems at baseline and further reports 'sleeping problems' during follow up, then 'sleeping problems' will not be counted as adverse events.

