A decision on medical and scientific grounds is required to assess whether an immediate notification of an event is warranted in other situations, such as medically important events which are not life-threatening, fatal or cause hospitalization, but could endanger the patient or required an intervention to prevent one of the above conditions developing.

Remark: Examples of such events are intensive care in the emergency room or at home to treat a bronchospasm; convulsions not causing hospitalisation, or the development of drug addiction or drug abuse.

Monitoring of AEs (including SAEs)

The Site Principal Investigator (PI) will make a causality assessment. He should be informed about any new data on a participant for whom a causality link had already been established to reconsider its analysis and if necessary reassess the causality. Data shall only be modified following an official query procedure. Source Document review meetings shall be organised regularly, during which the site PI and the local study team shall review AE data (intensity, causality, and date of event manifestation in relation to the start of treatment). Safety data should be entered immediately in the eCRF.

A Medical Monitor will be available for the trial site to resolve arising safety related questions and uncertainties. He will oversee the medical aspects of the clinical trial and will actively collaborate with the sites. The medical monitor will have access to the eCRF and can address a request to the site PI concerned to add any further information needed for the safety analysis. The medical monitor will conduct the final review of the eCRF for any participants who have had an adverse event.

Obligation of AE and SAE notification

Adverse Events

The AEs, regardless of their seriousness and causal relationship to the study drug, arising between the first administration of study medication and the last study visit (as per the protocol), must all be recorded on the participant's Source Document (AE recording section). When possible, the symptoms must be regrouped within a single syndrome or diagnosis. The healthcare personnel shall have to specify the date of manifestation of the event, its intensity, final evolution, the measures taken and the treatment undertaken (if any).

Serious Adverse Events (SAEs)

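### The protocol exempts venepuncture-related presyncope from AE recording, against its own AE rules, so some post-dose light-headedness could escape causality review

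*Protocol*

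**What the plan says.** Under Potential risks for participants, the Phlebotomy paragraph names minor bruising, "local tenderness or presyncopal symptoms associated with venepuncture, which will not be documented as AEs if they occur". It gives no time window, no assessor and no criterion for deciding that a symptom belongs to the draw.

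The safety part of the protocol sets the opposite rule:

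- The definition of an adverse event covers a new sign, symptom or disease "temporally associated with the use of a medical treatment or procedure that may or may not be considered related" to that treatment or procedure.
- Obligation of AE and SAE notification says that "The AEs, regardless of their seriousness and causal relationship to the study drug", must all be entered in the source document if they arise between first dose and last visit.
- Monitoring of AEs gives the causality assessment to the site principal investigator. It provides for regular review of AE data by the site team, and for a final eCRF review by the medical monitor for participants who had an AE.

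The Praziquantel paragraph, next to the Phlebotomy paragraph, lists dizziness as a side effect at below 10%. On dosing days, the study drug section says "Before the medication is administered the following measures will be performed on all participant", and the list includes blood smears and blood for qPCR. It closes with "Afterwards study medication is administered". Table 2 repeats sampling every 6 hours to H66 and daily from D3 to D7.

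**The concern.** The exemption places an attribution decision before recording. If someone decides that a near-faint came from the needle, no AE entry exists, and the investigator and the medical monitor have nothing to assess. Elsewhere the order is reversed: record first, then judge the cause.

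This matters because light-headedness has two possible sources in this trial, the draw and the drug. Procedures are the same in both arms (Allocation of the groups), so genuine venepuncture reactions drop out equally in expectation. A drug-caused episode credited to a draw can drop out only from the praziquantel arm. At stake is secondary endpoint 3, the occurrence of AEs on praziquantel versus placebo, in a trial with 22 participants per arm.

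**Working it through.** **1. The two rules side by side.** Take a participant who feels faint after a study blood draw on D1. Under the AE definition, the event is new and follows a procedure, so it is an AE. Under the notification section, it arises after first dose and is recorded whatever its cause. Under the Phlebotomy paragraph, it is not documented as an AE. All three statements cannot be followed. No other section ranks them or makes one an exception to another.

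**2. How often a draw is near.** Table 2: 1 at screening + 12 from H0 to H66 + 5 on D3 to D7 = 18 scheduled samplings. Two (screening and H0) precede the first dose, leaving 16 after it.

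**3. When a drug effect could be confused with a draw.** The rationale section gives peak plasma level at 1–3 h, a half-life of 0.8–1.5 h for the parent drug and 4.5 h for metabolites. With simple first-order decay counted from the dose (a simplification that ignores absorption), the fraction left is 0.5^(t / half-life):

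| Time after dose | Parent drug | Metabolites |
|---|---|---|
| 4 h (early end of H6 ± 2 h) | 3.1% to 15.8% | 54% |
| 8 h (late end of H6 ± 2 h) | 0.1% to 2.5% | 29% |
| 24 h (next pre-dose draw) | about 0% | 2.5% |

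A reaction during the H0 draw cannot be a drug effect, and one during the H24 or H48 pre-dose draw is unlikely to be. The overlap lies around the draw 4–8 h after dosing, and in the hours after the pre-dose draw if a symptom near the drug peak is traced back to it.

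**4. Scale.** The protocol states no figure to reproduce here. With n = 22 on praziquantel and a true dizziness rate p, the expected number of participants is 22p, and the chance of at least one is 1 − (1 − p)^22. The listed rate is only a ceiling, so the 5% and 1% rows are assumptions:

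| p | 22p | P(at least one) |
|---|---|---|
| 10% | 2.2 | 0.90 |
| 5% | 1.1 | 0.68 |
| 1% | 0.22 | 0.20 |

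If a fraction m of these cases were credited to a draw, the expected loss would be 22 × p × m. The documents give no value for m. At p = 10% the loss is 0 for m = 0, 1.1 for m = 0.5 and 2.2 for m = 1. At p = 1% it is never above 0.22.

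**The case against.** The strongest reply is that the exemption is a deliberate and open rule about minor, foreseeable reactions to sampling, and can be read as a specific exception to a general definition. The definition would equally catch bruising and tenderness, which few would insist on recording. This has force as a reading, but the protocol does not say it, and the notification section admits no exceptions. The practical difference is that bruising and tenderness at the puncture site resemble no listed praziquantel effect, whereas presyncope resembles one.

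Other safeguards are real. AEs are asked about at every visit from H0. Apart from the physician giving treatment, study physicians are blinded, so knowledge of allocation should not steer attribution. A source note is not forbidden. Blinding does not remove the bias, however, because it arises from the drug effect existing in one arm only.

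A reader might infer more than the text supports:

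- **That dizziness and drowsiness are discarded.** Neither is exempt as such. Only presyncopal symptoms linked to venepuncture are, and drowsiness is not near-fainting.
- **That any dizziness on D0–D2 has a draw to explain it.** The timing above is against this. The peak at 1–3 h falls between draws, and other checks are listed between the pre-dose sample and the dose.
- **That a first sign of arrhythmia would go unescalated.** The paragraph waives AE documentation, not care. Pulse and blood pressure are taken at each visit, abnormal findings must be assessed, and an independent medical monitor is on site. At the listed rate below 0.0001%, fewer than 22 × 0.000001 = 0.000022 cases are expected.
- **That most of the dizziness signal would vanish.** This needs both the ceiling rate and near-total misattribution, and the documents support neither assumption.

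The comparison is also weak even with full recording. Two of 22 against none of 22 gives a two-sided Fisher p of 2 × 231/946 = 0.49, and the Statistics section plans descriptive summaries for secondary endpoints.

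**Conclusion.** The contradiction stands on the text alone and needs no assumption: the Phlebotomy paragraph cannot be followed together with the AE definition and the notification duty. Its consequence is a modest bias risk in one direction, confined to secondary endpoint 3. It rests on two assumptions: that presyncope and dizziness can be confused in practice, and that some drug-caused episodes would be credited to a draw. The most that could be lost is about 2 expected cases among 22, at the ceiling rate and with every case misattributed. The likely loss is smaller and cannot be determined from the documents. The primary endpoint is unaffected.

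**What to change.** Reconcile the Phlebotomy paragraph with the AE definition and the notification section:

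- Limit the exemption to local puncture-site findings (minor bruising, local tenderness), and name it in the safety section as the one exception.
- Record presyncope, dizziness and syncope as AEs, with the times of the last dose and the last draw and a procedure-related flag. Table 4 already asks for other possible aetiologies to be noted for events graded possible, and venepuncture belongs there.
- Tabulate procedure-related events separately by arm, so that they do not crowd the drug safety summary.

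The cost is one changed sentence with a matching line in the safety section and a small CRF addition. The downside is a few extra minor AEs in both arms.

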To calculate the sample size, we estimated that only 10% of participants in the placebo group will have a parasitemia below the microscopic limit of detection on day 7 versus 50% in the intervention group. With a power of 80% and an alpha error of 5% and considering a ratio 1:1 (treatment versus placebo group), we need 20 subjects in the placebo group and 20 subjects in intervention group. Accounting for a possible dropout rate of 10% in each study arm the final sample size will require recruitment of a total of 44 subjects.

Endpoints and assessment methods

Primary endpoint:

Parasitemia undetectable by thick blood smear on D7 after the start of administration of study drugs

Assessment method: Light microscopy

All those needing rescue treatment according to the physicians' judgement before day 7 will be counted as treatment failures together with all positives at day 7.

Secondary endpoints:

1) Parasitemia reduction $\geq 90\%$ on D7 compared with baseline assessed by light microscopy of thick blood smears

Assessment method: Light microscopy

2a) Time to parasitemia level < 100 parasites/ μl in the PZQ 3-day treatment group versus placebo assessed by microscopy

Assessment method: Light microscopy

2b) Time to parasitemia level below microscopic limit of detection in the PZQ 3-day treatment group versus placebo assessed by microscopy

Assessment method: Light microscopy

3) Occurrence of adverse events (AEs) in the PZQ 3-day treatment group versus placebo

Assessment method: Clinical examination and laboratory analysis

4) Time to parasite clearance assessed by qPCR in the PZQ 3-day treatment group versus placebo

Assessment method: Quantitative PCR

5) Parasitological cure rate assessed by qPCR on D7 after administration of study drugs

Assessment method: Quantitative PCR

6) Area under the curve (AUC) of microscopically-determined parasite mass between D0 and D7 in the PZQ 3-day treatment group versus placebo

Assessment method: Light microscopy

Exploratory endpoints

Proportion of participants with detectable gametocytes during D3-D7 in the treatment group versus placebo

Assessment method: Light microscopy

Duration of the study

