Participants will not benefit directly from participation in this study. The only benefits for the participants will be information about their general health status and the treatment from the *Plasmodium falciparum* infection in the end of the follow up. However, it is hoped that the information gained from this study will contribute to the development of safe and effective antimalarial drug. Compensation for missed working day if any and transportation fee for follow-up visit will be reimbursed.

Recruitment and withdrawal of trial participants

Participants

The study is designed as a randomized placebo-controlled assessor-blinded clinical trial to assess the safety and efficacy of praziquantel to treat *Plasmodium falciparum* infections in asymptomatic subjects in an endemic area of Gabon. Potential adult participants living in CERMELE's catchment areas in Gabon will be screened for parasitemia of 200 to 5000 pf/μl without malaria signs for inclusion into the clinical trial.

Informed Consent

All participants will sign and date the informed consent form before any study specific procedure is performed. At the screening visit, the volunteer will be fully informed of all aspects of the trial, the potential risks and their obligations. The following general principles will be emphasized:

- Participation in the study is entirely voluntary
- Refusal to participate involves no penalty or loss of medical benefits
- The participant may withdraw from the study at any time
- The participant is free to ask questions at any time to allow him or her to understand the purpose of the study and the procedures involved

The aims of the study and all tests to be carried out will be explained. The volunteer will be given the opportunity to ask about details of the trial and will then have time to consider whether or not to participate. Potential participants will be asked to sign and date two copies of the consent form, one for them to take away and keep, and one to be stored in the Investigator's File. These forms will also be signed and dated by the Investigator.

Inclusion Criteria

The subject must satisfy all the following criteria to be eligible for the study:

- Subject male or female with age ≥ 18 years
- *Plasmodium* parasitaemia with 200 to 5000 parasites/ μL

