- Asymptomatic malaria defined by: presence of *Plasmodium* parasites with absence of fever (axillary temperature ≤ 37.5 ° C or oral / tympanic temperature ≤ 38 ° C, or absence of history of fever in recent 24 hours and the week before inclusion).
- Written informed consent must be obtained before any study assessment is performed.
- Willingness not to take drugs or substances which could have an impact on praziquantel blood levels. The timeframe for the abstinence of these drugs will be 2,5 days before and 2,5 days after intake of praziquantel or will be individually calculated by the study team, if necessary.
- Women only: Must agree to practice continuous contraception for the duration of the study. Those methods include: combined (estrogen and progestogen containing) hormonal contraception, associated with inhibition of ovulation, oral, intravaginal or transdermal progestogen-only hormonal contraception associated with inhibition of ovulation, oral, injectable, implantable intrauterine device (IUD), intrauterine hormonereleasingsystem (IUS), bilateral tubal occlusion, vasectomised partner, sexual abstinence and use of condoms.

The following is a selection of drugs/substances to be avoided: Tacrolimus, Ciclosporin, Sirolimus, Cyclophosphamid, Erlotinib, Gefitinib, Doxorubicin, Etoposid, Vindesin, Vinblastin, Tamoxifen, Clotrimazol, Miconazole, Ketoconazol, Itraconazol, Clarithromycin, Erythromycin, Amitriptylin, Clomipramin, Imipramin, Citalopram, Escitalopram, Fluoxetin, Norfluoxetin, Sertralin, Aripiprazol, Haloperidol, Risperidon, Ziprasidon, Alfentanil, Codein, Fentanyl, Methadon, Alprazolam, Clonazepam, Flunitrazepam, Midazolam, Triazolam, Pimozid, Atorvastatin, Lovastatin, Simvastatin, Amlodipin, Diltiazem, Felodipin, Nifedipin, Verapamil, Sildenafil, Tadalafil, Buspiron, Venlafaxin, Amiodaron, Ivabradin, Rifampicin, Chinolone, Phenytoin, Carbamazepin, Oxcarbazepin, Phenobarbital, Primidon, Modafinil, Dexamethason, Telithromycin, Chloramphenicol, Fluconazol, Ketoconazol, Itraconazol, Ritonavir, Indinavir, Nelfinavir, Verapamil, Aprepitant, Nefazodon, Amiodaron, Cimetidin, Chloroquine, Abametapir, Aprepitant, Clofazimin, Deferasirox, Erdafitinib, Fosaprepitant, Fusidic Acid, Ivosidenib, Sarilumab, Siltuximab, Simeprevir, Stiripentol, Tocilizumab, Hypericum

("Johanniskraut"), Ginger ("Ingwer"), Garlic ("Knoblauch"), Liquorice ("Lakritz"), Grapefruit, Valeriana ("Baldrian"), Turmeric ("Gelbwurzel"), Ginseng.

Exclusion Criteria

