The subject may not enter the study if any of the following apply:

- Signs and symptoms of complicated malaria / severe malaria
- Taking an experimental drug in the last 4 weeks.
- Any antimalarial treatment in the last 4 weeks
- Is using and intends to continuing using a medication known to cause drug reactions with artemether/lumefantrine (e.g. cimetidine, metoclopramide, antacids, kaolin, terfenadine etc.)
- Use of systemic antibiotics with known antimalarial activity within 30 days of study enrolment (e.g. trimethoprim-sulfamethoxazole, doxycycline, tetracycline, clindamycin, erythromycin, fluoroquinolones, or azithromycin).
- Use of praziquantel within 30 days of study enrolment.
- Previous (within the last 10 years) participation in a malaria vaccine study
- Moderate to severe anemia (Hemoglobin level < 8 g/dL)
- Known history of hepatic disease or liver damage
- Any confirmed or suspected immunosuppressive or immunodeficient condition, including human immunodeficiency virus (HIV) infection
- Use of immunoglobulins or blood products within 3 months prior to enrolment
- Contraindications or known allergy to praziquantel or the first-line anti-malarial medication artemether/lumefantrine, or known or suspected allergy or intolerance to any other ingredient of the drug products (IMP/Non-IMP)
- Severe malnutrition (Body Mass Index (BMI) < 16.0)
- Pregnancy, lactation or intention to become pregnant during the study
- Known history of sickle cell anaemia, sickle cell trait, thalassemia or thalassemia trait
- Participants unable to be closely followed for social, geographic or psychological reasons
- Any other significant disease, disorder or finding which, in the opinion of the investigator, may significantly increase the risk to the participant because of participation in the study (e.g.

renal transplantation), affect the ability of the participant to participate in the study or impair interpretation of the study data.

Withdrawal of Participants

In accordance with the principles of the current revision of the Declaration of Helsinki (updated 2013) and any other applicable regulations, a participant has the right to withdraw from the study at any time and for any reason, and is not obliged to give his or her reasons for doing so. The Investigator may withdraw the participant at any time in the interests of the participant's health and well-being. In addition, the participant may withdraw/be withdrawn for any of the following reasons:

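### The asymptomatic inclusion criterion joins current temperature and fever history with 'or', so a person afebrile at screening with fever in the past day or week is eligible

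*Protocol*

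**What the plan says.** The bullet in the protocol's Inclusion Criteria requires "presence of *Plasmodium* parasites with absence of fever". A bracket then explains absence of fever: an axillary limit of 37.5 °C or an oral/tympanic limit of 38 °C, followed by "or absence of history of fever in recent 24 hours and the week before inclusion". The Synopsis (Main inclusion/exclusion criteria) has the same bracket.

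Other places that bear on it:

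- Inclusion Criteria, opening line: "The subject must satisfy all the following criteria to be eligible for the study".
- Participants: adults are screened for parasitaemia of 200 to 5000 per µl "without malaria signs for inclusion into the clinical trial".
- Exclusion Criteria: the only malaria-illness exclusion is "Signs and symptoms of complicated malaria / severe malaria". The last bullet leaves to judgement "Any other significant disease, disorder or finding which, in the opinion of the investigator, may significantly increase the risk to the participant", or a finding that would hinder participation or interpretation of the data.
- Treatment of *Plasmodium falciparum* Infection: one trigger for stopping study treatment and giving rescue is "Any parasitaemia based on microscopy with fever post-dose".
- Endpoints and assessment methods: "All those needing rescue treatment according to the physicians' judgement before day 7 will be counted as treatment failures", together with everyone positive on day 7.

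**The concern.** The bracket contains two uses of *or*. The first separates measurement sites and is harmless. The second makes current temperature and fever history alternatives, so meeting either is enough. A criterion meant to describe people without symptoms then accepts someone who was febrile the day before, provided the thermometer reads normal at screening.

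Two things are at stake. First, the enrolled population may not be the one named in the title, aim and study population. Enrolling a recently febrile person would not be a deviation, so a strict screener and a literal screener could enrol different people from the same queue. Second, fever feeds into the primary endpoint through the rescue rule. If fever returns after dosing while any parasites are visible, the participant is rescued and counted as a failure, whatever the drug would have done to the parasites by day 7. With 22 per arm, two such participants are 2/22 = 9% of an arm.

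**Working it through.** **1. The criterion as logic.** Let A = temperature within the limit at screening (either site), and B = no fever in the last 24 hours and the preceding week. The bracket as written is A or B; a joint condition is A and B.

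| Now | History | As written (A or B) | Joint (A and B) |
|---|---|---|---|
| afebrile | no fever | eligible | eligible |
| afebrile | recent fever | eligible | not eligible |
| febrile | no earlier fever | eligible (literal reading only) | not eligible |
| febrile | recent fever | not eligible | not eligible |

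Whenever A is true the outcome does not depend on B, so the history clause never excludes an afebrile person. The second row is the point. The third row is weaker and is taken up under the objection.

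**2. Whether another rule closes the second row.** The requirement to meet all criteria works between bullets, and this *or* lies inside one bullet. The severe-malaria exclusion does not cover an uncomplicated fever that has settled. The statement under Participants about malaria signs is narrative rather than a listed criterion, and a person can be free of signs at screening after a recent fever. The last exclusion bullet could be used, but it is discretionary and mentions neither fever nor fever history.

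**3. The plan's own sample size.** Inputs from the Sample size section: 10% versus 50% clearance, power 80%, alpha 5%, ratio 1:1. Sidedness is not stated; two-sided is assumed. With pooled variance and no continuity correction (mean rate 0.30):

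n = [1.960·√(2·0.30·0.70) + 0.842·√(0.10·0.90 + 0.50·0.50)]² / 0.40² = [1.270 + 0.491]² / 0.16 = 19.4, that is 20 per arm.

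This reproduces the stated 20. The stated total of 44 is 40 × 1.10. The point does not challenge these figures.

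**4. Illustration of the effect on power.** Let f be the share of a whole arm that is rescued for fever before day 7 and would not have been otherwise. It is taken as equal in both arms and unrelated to clearance. The success rates become 10%·(1 − f) and 50%·(1 − f). The protocol gives no value for f, so a range is shown. Power is the exact binomial power of the uncorrected chi-square test at two-sided 5%, chi-square being the test named under Statistics.

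| f | Rates | 22 per arm | 20 per arm |
|---|---|---|---|
| 0 | 10% v 50% | 0.864 | 0.838 |
| 10% | 9% v 45% | 0.811 | 0.775 |
| 20% | 8% v 40% | 0.746 | 0.702 |

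**The case against.** The strongest reply is that the intent is plain. The lead words of the bullet require absence of fever, the narrative asks for people without malaria signs, and investigators would probably apply the strict reading or use the discretionary exclusion. Recent antimalarials and several antibiotics are also excluded, which removes some people treated for a recent fever. This makes the fault one of drafting against a documented intent and limits its likely practical effect. It does not cure the text: eligibility is checked against the written criterion, and the written criterion admits the afebrile person with recent fever.

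Four stronger readings are tempting, and the documents do not support them.

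- *A person febrile at screening is equally eligible.* The literal *or* allows it, but it conflicts with the lead words. Screening takes place within 24 hours of dosing, so a fever measured then is naturally read as fever in the recent 24 hours and fails the history limb too.
- *Nothing in the exclusions could catch these people.* The discretionary bullet could, case by case.
- *Recent fever means early symptomatic malaria.* The protocol does not say so. Fever in the past week in an adult who is now afebrile may have another cause, and the step from past fever to fever after dosing is an assumption.
- *Recently febrile participants would be left without protection.* They are in hospital for at least three days, with vital signs and smears every six hours to H66 and daily visits afterwards. Rescue is available throughout, and all participants receive antimalarial treatment at day 7.

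**Conclusion.** The point holds for one group: people afebrile at screening with fever in the last 24 hours or week. For them the stated rule, in both places where it appears, contradicts the protocol's own population. This follows from the wording alone and needs no assumption.

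The size of the effect on the result is not known. The power figures rest on an assumed f, which is not the share admitted through the *or*. It is the smaller share who are admitted that way, then become febrile with parasites after dosing, and are rescued before day 7. The figures also treat the planning rates of 10% and 50% as free of rescue failures, which the Sample size section does not say. At f = 10% power stays just above the planned 80% with 22 per arm (81%) and falls just below it with 20 (78%). A reader might infer that the trial is underpowered because of this wording; the documents do not show that. The case for correcting it is that the criterion defines who is in the trial and the correction is very small.

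**What to change.** In the Inclusion Criteria and in the Synopsis, replace the last *or* in the bracket with *and*, so that the temperature limb and the fever-history limb are both required. Keep the *or* between the axillary and the oral/tympanic limits. This brings the criterion into line with the asymptomatic population stated elsewhere in the protocol, and it also removes the weaker literal reading about people febrile at screening. The rescue and endpoint rules need no change for this purpose.

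The cost is one word in two places and possibly a slightly higher screen-failure rate. It is best settled before enrolment.
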